effective treatment for depression in younger [Krogh et al., 2011] and older adults [Blake et al., 2009]. Importantly, exercise also addresses vascular risk factors thought to be particularly relevant to aging (Blaha et al., 2016), in general, as well as depression in late life [Alexopoulos et al., 2006, Sheline et al., 2010]. While there have been several studies demonstrating the benefits of exercise on depression in older adults, no known study has examined the positive benefits of a structured, group exercise program on mood and well-being in an aging sample. As an ancillary aim, we will also examine the impact of a structured exercise intervention on cognitive functioning. Fit and Strong!, a physical activity / behavior change program for older adults with lower extremity osteoarthritis, has demonstrated efficacy, effectiveness, and ease of dissemination for individuals with osteoarthritis living in the community [Hughes et al., 2004, 2006, 2010]. The goal of this study is to adapt Fit & Strong! for increasing positive affect and reducing negative affect and depressive symptoms among older adults residing in the community.

C. Research Design and Methods

C.1 General study design

We will enroll 40 subjects in this study between the ages of 60 and older, from the community who score at least 1 on the Patient Health Questionnaire-8 (PHQ). Up to 20 participants will have PHQ-8 scores of 1-4, while up to one-half of participants will have PHQ scores >4. At the outset of the study, up to 20 individuals will be randomly assigned to the intervention portion of the study, while up to 20 individuals will be randomly assigned to a crossover wait-list group, who will undergo the intervention beginning at study week 10. Outcome measures will be administered to all participants before the intervention and to the intervention group after they undergo the intervention. The wait-list group will complete all of their outcome measures before they begin the intervention(see Figure 1).

Figure 1

C.2 Phone screen and Study Visits

C2.1 Pre-Study Screen:

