C2.3. Exercise Intervention. Participants will be invited back to Oakwood Shores for an 8-week physical activity/behavior change intervention. The intervention will consist of the Fit and Strong! program adapted to address the impact of exercise on enhancing positive affect and reducing negative affect and depressive symptoms. Exercise classes will meet three times per week for 90 minutes per session for eight weeks. Each class is divided into 60 minutes of strength training, flexibility, and cardiovascular exercise and 30 minutes of group education/discussion, which has been adapted to include affect-oriented content. An outline of education topics for each of the 24 sessions can be found in Section C.7. Two sessions of Fit and Strong! will be delivered as part of the study; each will be limited to 20 participants. Classes will be taught by certified exercise instructors who will undergo 8-hours of training on the Fit & Strong! Program. The instructor will be trained to deliver depression specific content by a clinical psychologist Program fidelity will be monitored with the Fit and Strong! Plus Implementation Checklist and observation of the intervention by study investigators during one Fit & Strong class per 8-week session. During the intervention, participants will complete a medication adherence and group cohesion measure at baseline, 4 weeks, and 8 weeks.

C2.4. Debriefing Session: Following the intervention, a debriefing session will be held with all intervention participants. This session will be used to adapt Fit & Strong! for future study, addressing issues around affect and treatment effectiveness.

C2.5. Post-Intervention Measures. During Week 9, participants will undergo the same interview, self-report questionnaires (only those bolded in section C.6.3), mobility assessment, and

neuropsychological tests they completed during the baseline visit. Participants that were involved in the MRI testing component will also undergo the same testing for post-intervention results.

C.3 Subject Payment

All participants enrolled in the study (intervention and crossover wait list group) will be paid \$20 upon completion of their baseline interview and \$35 upon completion of their post-test. Participants will be paid in cash. Participants involved in the MRI testing will be paid \$50 in cash upon completion of the scan pre-intervention and post-intervention (\$100 total).

C.4 Entry Criteria for Studies

C.4.1 Inclusion Criteria:

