machine will produce imaging of each participant's brain. Participants will be allowed to request earplugs to wear during the procedure, as the machine is quite noisy. In the case that a participant should start to feel claustrophobic, the MRI testing will be stopped immediately. The total time each participant will be asked to stay inside the machine should be no more than an hour. MRI testing will take place at baseline before the exercise intervention and after the intervention (week 9). A taxi will be provided to and from the imaging center for participants that need it. Participants will be paid \$50 at each session (\$100 total).

C 6.7. Data Analysis/Interpretation: Participation rates and program acceptability ratings will be quantified. Changes in depressive symptoms and positive and negative affect will be analyzed using a repeated measures ANOVA model. Between-group analyses will be conducted to determine whether significant changes occur in the outcomes between baseline, 9- and 18-weeks to examine maintenance effects over time. A mixed-effects model will be used to determine whether intervention participants significantly increased their participation in physical activity between baseline and 9- and 18-weeks. Within-group analyses will also be conducted to determine whether participants improved in depressive symptoms, positive and negative affect, and physical activity between baseline, immediately following Fit & Strong! participation, and 2 months post-Fit & Strong! participation. Finally, the Baron and Kenny Causal Steps approach [Baron and Kenny, 1986] will be used to determine whether change in physical activity between baseline and immediately post Fit & Strong! mediates the decrease in depressive and positive and negative affect. A process evaluation will be conducted to measure aspects of program implementation including fidelity, intervention dose received, participant attrition, and program acceptability ratings. [Washburn et al., 1993; Miller et al., 1992; Bellamy, 1989; Hughes et al., 1991; Resnick and Jenkins, 2000] See Appendix C. [Maust et al., 2013; van Loon et al., 2013]

C 6.8. Data and Safety Monitoring Plan

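### The intervention arm appears to be taught as one class, but C 6.7 neither allows for shared class outcomes nor limits Aim 2 to that class

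*Combined protocol and SAP*

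**What the plan says.** Section C.1 allocates participants individually: "up to 20 individuals will be randomly assigned to the intervention portion of the study", and "up to 20 individuals will be randomly assigned to a crossover wait-list group, who will undergo the intervention beginning at study week 10". Section C2.3 sets the delivery: "Two sessions of Fit and Strong! will be delivered as part of the study; each will be limited to 20 participants". A session here is an eight-week course, since the fidelity text in C2.3 and C.7.2 speaks of one observed class in each eight-week session.

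The teaching is a group activity. Each 90-minute meeting, three times a week, includes "30 minutes of group education/discussion, which has been adapted to include affect-oriented content", and "participants will complete a medication adherence and group cohesion measure at baseline, 4 weeks, and 8 weeks".

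Section C 6.7 says that changes in depressive symptoms and in positive and negative affect "will be analyzed using a repeated measures ANOVA model", with between-group tests for significant change. It names no class or instructor term, no clustering, no ICC, and no limit on how far the result generalises. The group cohesion measure has no role in the analysis.

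**The concern.** People who spend eight weeks in the same discussion group with the same teaching staff can be expected to share part of their outcome. The shared content is about affect and mood, which are the Aim 2 outcomes. A standard repeated measures ANOVA treats participants as independent. Here the possible dependence sits in one arm only: the treated arm is one class, and the wait-list is not yet grouped at week 9.

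Two things are at stake if the result is read as evidence about the programme. First, the stated precision of the 9-week contrast is too good. Second, a class that happened to go well or badly, or the staff who taught it, would be counted as programme effect, and nothing in the data could reveal this.

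**Working it through.** The plan gives no power, alpha, SD, ICC or sample-size derivation, so there is no figure of its own to reproduce.

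**Step 1: is it one class?** There are two eight-week sessions of at most 20 people (C2.3). The wait-list of up to 20 starts at week 10 (C.1) and needs one of them. That leaves one session for up to 20 intervention participants before week 9. This is a deduction; the protocol does not say it in words.

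**Step 2: inputs.**
- Class size m: 20 as randomised (C.1), or 13 after the 33% non-completion in C.5.2 (20 × 0.67 = 13.4).
- Wait-list: the same number, unclustered.
- Alpha: 0.05 two-sided (assumed).
- Total variance of the change score: 1 in each arm (a scaling).
- ICC of the change score: 0.01, 0.05 and 0.10 (assumed).

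With two time points, the group-by-time test in the ANOVA is the two-sample t test on change scores, so that test is used here.

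**Step 3: formulas.**
- True variance of the difference, for inference across classes: V = [1+(m−1)ICC]/m + 1/m.
- Variance the naive analysis estimates: V₀ = [(1−ICC) + 1]/m. The spread within a single class does not contain the class effect, so it shows only (1−ICC) of the total.
- Standard error ratio: R = √(V/V₀) = √{[2+(m−1)ICC]/(2−ICC)}.
- Actual type I error: 2·P(T > t*/R), with 2m−2 degrees of freedom and t* the two-sided 5% critical value.

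Worked case, m = 13 and ICC 0.05: R = √[(2+0.60)/(2−0.05)] = √(2.60/1.95) = √1.333 = 1.155.

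**Step 4: results.** Half-widths are for a 95% interval, in SD units, with t* = 2.064 (24 df) or 2.024 (38 df).

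| m | ICC | R | Type I, t approx. | Type I, simulated | Half-width, naive | Half-width, required |
|---|---|---|---|---|---|---|
| 13 | 0.01 | √(2.12/1.99) = 1.032 | 5.7% | 5.7% | 0.81 | 0.83 |
| 13 | 0.05 | √(2.60/1.95) = 1.155 | 8.7% | 8.7% | 0.80 | 0.92 |
| 13 | 0.10 | √(3.20/1.90) = 1.298 | 12.5% | 12.5% | 0.79 | 1.02 |
| 20 | 0.01 | √(2.19/1.99) = 1.049 | 6.1% | 6.3% | 0.64 | 0.67 |
| 20 | 0.05 | √(2.95/1.95) = 1.230 | 10.8% | 10.8% | 0.63 | 0.78 |
| 20 | 0.10 | √(3.90/1.90) = 1.433 | 16.6% | 16.6% | 0.62 | 0.89 |

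The simulation used 100,000 two-sample t tests per row.

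**Step 5: confounding.** With one class in the treated arm, the between-class variance has 1 − 1 = 0 degrees of freedom. The ICC cannot be estimated and a random class term cannot be fitted. A class one standard deviation better than average would move the observed effect by √ICC, which is √0.01 = 0.10, √0.05 = 0.22 or √0.10 = 0.32 SD.

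**The case against.** - **Randomisation is individual, so the test is valid.** This stands for the strict null. If attending affects no one, there is no class effect and the test stays near 5%. A reader might infer that the type I error is inflated whatever the question. That is not supported: the figures above apply only when the target is the average effect over classes that might have been run. For the effect of this one class, the naive standard error is closer to adequate.
- **The size rests on an assumed ICC.** This stands. Group discussion and a cohesion measure make a positive ICC plausible, but they do not show that it is 0.05 or 0.10. At 0.01 the effect is trivial.
- **The plan promises no confidence intervals, and Hypothesis 2 is judged on effect size.** This stands in part. It would be wrong to say that planned intervals are too narrow, because none are planned. But C 6.7 tests for significance, any interval later put around the effect size would use the same standard error, and step 5 shows that the effect size itself carries the class effect.
- **Delivery is standardised.** Training, a fidelity checklist and an observed class bear on how far staff may differ. They do not make classmates' outcomes independent.
- **This is a pilot.** Aim 2 asks only for a first look at efficacy, which lowers the consequence. It still makes a between-arm claim.

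A reader might also infer that a single instructor is confounded with the programme. The text does not establish this. C2.3 says "Classes will be taught by certified exercise instructors who will undergo 8-hours of training on the Fit & Strong! Program", then uses the singular in the next sentence, and never gives the number per class.

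**Conclusion.** The point holds as a cheap improvement, not as a flaw that invalidates the trial. For inference to the programme, the naive standard error is too small for any positive ICC. Over the assumed range, a nominal 5% test runs at about 6% to 13% with 13 completers and about 6% to 17% with 20. Whatever the ICC, class and teaching staff cannot be separated from programme at week 9.

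This rests on three things: the deduction that each session is one class; a positive ICC for the change score, whose value the documents do not give; and a reader who wants to generalise beyond this class.

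**What to change.** Keep the planned ANOVA and add two items to C 6.7.

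1. **A sensitivity table.** For each Aim 2 outcome, repeat the 9-week contrast of change scores. Multiply the observed intervention-arm variance of the mean by [1+(m−1)ICC]/(1−ICC), and leave the wait-list variance as observed. Use ICCs of 0.01, 0.05 and 0.10, defined for the change score, with m the number of class members analysed. The multipliers are 1.12/0.99 = 1.131, 1.60/0.95 = 1.684 and 2.20/0.90 = 2.444 at m = 13. At m = 20 they are 1.19/0.99 = 1.202, 1.95/0.95 = 2.053 and 2.90/0.90 = 3.222. The usual design effect without the division by (1−ICC) would under-correct.
2. **A scope statement.** Aim 2 conclusions apply to this one class and whoever taught it.

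No pass-or-fail ICC should be attached to the table, because nothing in the documents supports a particular cut-off.

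The cost is a few lines of analysis, with no new participants, classes or staff. The downside is wider reported uncertainty and reliance on an assumed ICC.

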Enhancing Well-Being Through Exercise During Older Age

NCT04536727

1/23/2019

“Enhancing Well-Being Through Exercise During Older Age”

Principal Investigator:

[name]
[contact]

Sponsors:

The Midwest Roybal Center for Health Promotion and Translation Pilot Grant Program

Study Locations:

The University of Illinois at Chicago
[name]

Oakwood Shores
[name]

Table of Contents

	Page
Table of Contents.....	2
A. Specific Aims.....	3
B. Background and Significance.....	3
C. Research and Design Methods.....	4
D. Protection of Human Subjects.....	11
Citations.....	14
Table 1.....	16

Research Protocol for “Enhancing Well-Being Through Exercise During Older Age”

Primary Investigator: [name]

Sponsor: The Midwest Roybal Center for Health Promotion and Translation Pilot Grant Program
Protocol Version 22

1/23/2019

A. Specific Aims

AIM 1. Determine the feasibility of adapting Fit and Strong! to include affect and mood-related content and employing this intervention among older adults with a range of depressive symptoms.

HYPOTHESIS 1. Participants will demonstrate **(1a)** adherence to the Fit & Strong! intervention defined as attendance at two-thirds or more of the exercise sessions over a 8-week period and **(1b)** acceptability of the Fit & Strong! intervention as a way to reduce depressive symptoms and improve positive affect and reduce negative affect, defined as at least 75% of participants reporting positive subjective opinions of the protocol during debriefing session assessments.

AIM 2. Begin to determine whether Fit & Strong! is efficacious as an approach for reducing depressive symptoms and improving positive affect and reducing negative affect among older adults.

HYPOTHESIS 2. Compared to wait-list participants, intervention participants will report an improvement in positive affect and a reduction in negative affect and depressive symptoms at 9 weeks as measured by medium to large effect sizes.

AIM 3. We will explore the relationship between negative/positive affect and depressive symptoms and maintenance of physical activity between groups at baseline, and 9- weeks, in order to determine whether an improvement in positive affect and a reduction in positive affect is associated with an increase in physical activity.

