Exercise Assessment and Screening for You (Resnick, 2008) A self-report questionnaire assessing conditions that might prohibit someone from safely engaging in physical activity (2 minutes).

Six-Item Screener: (Callahan et al., 2002) A brief screen for cognitive impairment and dementia that includes three orientation items (year, month, day of the week) and delayed recall of three items. When a cut-off score of ≤ 1 error is used for diagnosing dementia, sensitivity is reported as 100.0 for community-dwelling elders. (2 minutes)

Patient Health Questionnaire (PHQ-8): A self-report questionnaire assessing symptoms of depression and appropriate for use when a clinician is not involved in the assessment.

C.6.2 Clinical Interview (Approximately 15 minutes)

World Health Organization Disability Assessment Scale (WHO-DAS-II; World Health Organization, 2000). A clinician-administered measure of functioning in six-domains (15 minutes).

C.6.3. Self-Report Questionnaires (approximately 50 minutes)

The composite list of questionnaires includes the following outcomes: health and disability status, depression and affect, physical activity, sleep and fatigue, falls, history, and balance confidence, stress and social/emotional well-being, mobility, and cognitive functioning.

Physical Activity Scale for the Elderly (PASE) [Washburn et al., 1993]. A measure of weekly physical activity (5 minutes).

Western Ontario and McMaster University Osteoarthritis Index [Bellamy et al., 1989]. Set of standardized questionnaires used to collect data on arthritis-specific symptoms using 24 parameters (5 minutes)

Self-Efficacy for Exercise Scale [Resnick and Jenkins, 2000]. A self-report questionnaire developed for older adults addressing expectations around self-efficacy regarding the ability to continue engaging in exercise in the face of hurdles to exercise (3 minutes).

Chronic Conditions: GERI-AIMS: Checklist of chronic medical conditions (3 minutes)

Cardiovascular Risk Factors Questionnaire: Adapted from the Guidelines of the American College of Sports Medicine, ACSM (2000),_A brief screening to determine subjects cardiovascular risk factors (5 minutes).

The Established Populations for the Epidemiologic Study of the Elderly (EPESE) Questionnaire: A Likert-type scale for rating of ability to complete basic and instrumental activities of daily living. (5 minutes)

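### No instrument named for week 9 is described as measuring depressive symptoms or negative affect, two of the three Hypothesis 2 outcomes

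*Combined protocol and SAP*

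**What the plan says.** Under Hypothesis 2 (section A), compared with the wait-list group, "intervention participants will report an improvement in positive affect and a reduction in negative affect and depressive symptoms at 9 weeks". Section C 6.7 plans a repeated measures ANOVA of all three outcomes and a mediation analysis of change in them.

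Section C.1 gives the general timing: "Outcome measures will be administered to all participants before the intervention and to the intervention group after they undergo the intervention". For the other arm, "The wait-list group will complete all of their outcome measures before they begin the intervention(see Figure 1"). The wait-list participants are those "who will undergo the intervention beginning at study week 10".

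Section C2.5 sets the content of the week-9 visit. It repeats the baseline interview, mobility assessment and neuropsychological tests, adds MRI for those who had it at baseline, and limits the remaining forms to "self-report questionnaires (only those bolded in section C.6.3").

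The only depression measure described in section C.6 is in C.6.1, under screening: "Patient Health Questionnaire (PHQ-8): A self-report questionnaire assessing symptoms of depression". C2.1 places it in the pre-study screen. The lead-in to C.6.3 lists depression and affect among the domains its questionnaires cover.

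**The concern.** Aim 2 is the efficacy aim, and depressive symptoms and negative affect are two of its three outcomes. C.1 says in general terms that outcomes are measured in both arms. C2.5 is the rule that staff would follow at the visit, and read literally it leaves out the only depression measure the protocol describes and supplies none for negative affect.

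If nothing elsewhere adds a scale, there would be no week-9 values on these outcomes in either arm. The wait-list arm is an untreated comparator only until week 10, so the controlled comparison could not be rebuilt later. The mediation analysis would lose the same variables.

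Using apathy, pleasure or stress scores instead would mean choosing the outcome after the fact, because the protocol does not designate any of them for this purpose.

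**Working it through.** **Instruments named for week 9.** I took each component that C2.5 lists and read the description of every instrument in the matching part of C.6. The optional MRI is left out of the count.

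| Component | Section | Instruments named | Described as measuring depressive symptoms | Described as measuring negative affect |
|---|---|---|---|---|
| Interview | C.6.2 | 1 | 0 | 0 |
| Questionnaires | C.6.3 | 14 | 0 | 0 |
| Mobility | C.6.4 | 5 | 0 | 0 |
| Neuropsychological | C.6.5 | 8 | 0 | 0 |
| Total | | 1 + 14 + 5 + 8 = 28 | 0 | 0 |

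The one interview named, the WHO-DAS-II, is described as a measure of functioning. The closest entries in C.6.3 cover apathy, pleasure, perceived stress, life satisfaction and six positive emotions. The last of these serves positive affect, if it is bold. The other two Hypothesis 2 outcomes have nothing.

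**Lost bold type.** The available text does not show which questionnaires are bold. The table counts all 14, which is the most favourable case, and the result is still zero.

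**Could an entry have dropped out of the list?** I summed the minutes stated for each instrument and compared them with the section headings.

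- C.6.2: 15, heading 15.
- C.6.3: 5+5+3+3+5+5+3+3+5+2+2+3+1+5 = 50, heading 50.
- C.6.4: 2+3+7+3+4 = 19, heading 19.
- C.6.5: 10+7+3+7+4+3+3+3 = 40, heading 40.
- Total: 15 + 50 + 19 + 40 = 124 minutes.

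All four match, so a lost entry with its own stated time is unlikely. An untimed entry cannot be ruled out: three of the four headings are approximate, and the PHQ-8 itself carries no time. In C.6.1 the other four screening items take 15+5+2+2 = 24 of the 35 minutes in the heading. That leaves 35 - 24 = 11 minutes, so the untimed PHQ-8 fits there.

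**Other places a scale might appear.** The reference list contains two depression scales, but no readable text schedules either. It also contains scales for fatigue, worry, anxiety and nicotine dependence that no assessment section names, so a citation does not show that a scale is given. C 6.7 names no instrument for either outcome.

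**The case against.** The strongest reply is that the schedule may sit in material we cannot read. C.1 points to Figure 1 for timing and C 6.7 refers to Appendix C. Neither is in the available text, and their absence here is not a fault of the plan.

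Section C.6 is also not a complete inventory. In C2.3, "participants will complete a medication adherence and group cohesion measure at baseline, 4 weeks, and 8 weeks", and neither measure is listed in C.6. C 6.7 cites an illness-burden scale that C.6 does not list. The C.6.3 lead-in also promises sleep, fatigue and falls, none of which has a listed instrument, so the list may simply be incomplete. The heading of C2.2 allows about 3 hours (its text says about two) against 124 named minutes. On the longer figure, 180 - 124 = 56 minutes, including consent, are unaccounted for. The repeated interview may be wider than the WHO-DAS-II, since D.1.2 and D.1.5 speak of diagnostic evaluations and interviews. Finally, 13 of the 28 instruments (5 mobility, 8 neuropsychological) would never be expected to measure mood.

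Much of this stands. The text does not prove that week-9 data would be missing, and the fairer denominator is the 14 questionnaires plus the interview, which gives 0 of 15. But none of it supplies a named scale. The lead-in shows an intention to measure depression and affect, and the list beneath it does not carry that out. Even if a scale is scheduled elsewhere, the readable text never says which instrument is the outcome.

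**Conclusion.** The concern holds. In the text available, 2 of the 3 Hypothesis 2 outcomes have no named week-9 instrument, in both arms (up to 20 participants each), and C2.5 as written omits the only depression measure that the protocol describes.

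The count does not depend on which questionnaires are bold. The loss of data does depend on two conditions: that C2.5 is followed literally, and that neither Figure 1, Appendix C nor an unnamed part of the interview adds a scale. I therefore hold the conclusion about lost data with medium confidence.

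The matter still has to be settled before participants reach week 9. The loss could not be repaired afterwards, and the outcome instrument is unspecified in either case.

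**What to change.** Reconcile C2.5, C.6.1 and C.6.3 with Hypothesis 2 and C.1:

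- List the week-9 questionnaires by name instead of by bold type.
- Give the PHQ-8, or another named depressive-symptom scale, at the post-consent baseline visit and at week 9 in both arms, and name it as the outcome. The screening score is a weaker baseline. It is taken before consent and is used for eligibility and score bands, so regression to the mean could affect the within-group analyses in C 6.7.
- Add one brief negative-affect scale at both visits, or remove negative affect from Hypotheses 2 and 3 and from C 6.7.
- If Figure 1 or Appendix C already schedules such scales, cite it in C2.5 and state which scale is the outcome.

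If the PHQ-8 is chosen, its floor should be noted. Under C.1, "Up to 20 participants will have PHQ-8 scores of 1-4", so up to half of the 40 can fall by at most 1-4 points. Reporting by entry band is optional.

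**Cost.** The protocol allows 2-3 minutes for scales of 5 to 10 items. Assuming the same for each new scale, the addition is 2 × 2 = 4 to 2 × 3 = 6 minutes per visit. Against the 124-minute baseline battery that is 4/124 = 3.2% to 6/124 = 4.8%. The week-9 percentage cannot be computed because the bolded subset is unknown. If the PHQ-8 took all 11 minutes left under the C.6.1 heading, the addition would be 13-14 minutes (11 plus 2-3). A protocol and IRB wording change is needed, but no extra visit and no extra participants.

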Recruitment will take place at the University of Illinois at Chicago campus, Oakwood Shores, clinics, churches, parks, free online community resources including Craigslist, and surrounding community areas. Recruitment will occur through advertisements about the study to individuals through printed brochures, flyers, news papers ads and announcements about the study. This will be followed by a telephone call where potential subjects can opt to go through the telephone or in-person screening process. The Resident Service Coordinator at Oakwood Shores will aid in the distribution of recruitment material and collection of names and numbers of potential

participants. The Resident Service Coordinator will not be responsible for conducting screenings or the collection of participant data, so will not be listed as authorized research personnel.

C.5.2 Attrition and Study Non-Completers/ Issue of Dropouts:

We estimate that 33% of subjects will not complete the protocol. While it would be optimal to have higher completion rate, this rate appears to represent the nature of the population. Subjects will also be financially compensated for each visit. Subjects will receive \$55 on via check delivered through the mail.. This payment will be in the form of a check and will be mailed to the participants' desired address. The following strategies for subject retention will be used: phone reminders/confirmation of visits, and established contact with the study coordinator. We will provide participants with a document that includes a list of scheduled appointments on the back. Based on these strategies, we anticipate that drop-out will be minimized to 33% of the sample.

C.6 Assessment of Subjects

C.6.1 Screening Measures (35 minutes)

Screening Form: This questionnaire asks respondents questions about medical and psychiatric history, related to the inclusion/exclusion criteria for this study. The screening form will be utilized prior to subject enrollment, either in person or over the phone, to determine if someone would be a good fit for participation in the study. (15 minutes)

MRI Screening Form: This questionnaire asks respondents questions about their medical history and willingness to participate in the MRI testing. The MRI screening will be given either over the phone, at the time of the general study screening, or in-person during the baseline visit (5 minutes).

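### Aim 2: repeated-measures ANOVA on baseline and week 9 is a change-score t-test, less precise than a baseline-adjusted week-9 comparison unless the correlation is about 0.9 or higher (equal SDs)

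*Combined protocol and SAP*

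**What the plan says.** Section C 6.7 gives the model for the Aim 2 outcomes: "Changes in depressive symptoms and positive and negative affect will be analyzed using a repeated measures ANOVA model". A separate sentence there plans between-group analyses over baseline, 9 and 18 weeks without naming a model. Neither C 6.7 nor any other section mentions ANCOVA or another baseline-adjusted comparison, and C 6.7 does not say how missing values are handled.

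Hypothesis 2 (section A) compares the intervention with the wait-list on positive affect, negative affect and "depressive symptoms at 9 weeks as measured by medium to large effect sizes".

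C.1 sets the measurement schedule: "Outcome measures will be administered to all participants before the intervention and to the intervention group after they undergo the intervention". For the controls, "The wait-list group will complete all of their outcome measures before they begin the intervention", and they are the group "who will undergo the intervention beginning at study week 10". C.3 provides payment for a baseline interview and a post-test in both arms: "All participants enrolled in the study (intervention and crossover wait list group) will be paid".

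On attrition, C.5.2 says: "We estimate that 33% of subjects will not complete the protocol".

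**The concern.** Only baseline and week 9 are available for the randomised contrast. With two arms and two visits, the group-by-time term compares mean change between arms. It takes the week-9 value minus the whole baseline value, so the baseline slope is fixed at 1. ANCOVA estimates that slope from the data. When the correlation is low or moderate, subtracting the full baseline adds noise to the comparison.

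The matter is precision, not validity: under randomisation with complete data, the change-score analysis is unbiased. Precision still counts here. The pilot enrols at most 40 people, expects a third not to complete, and judges Aim 2 by effect sizes. Those estimates and their intervals are what it hands to the next study.

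**Working it through.** **Inputs.** 40 enrolled, up to 20 per arm (C.1). 33% non-completion (C.5.2), so 40 × 0.67 = 26.8, about 27 analysed if every non-completer lacks week 9; this is the pessimistic reading. The documents give no SDs, correlation, alpha or power calculation, so there is no planned figure to reproduce. Assumed: correlation ρ of 0.3, 0.5, 0.7 or 0.9; equal SDs (set to 1) at both visits; 95% intervals; equal arms.

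**Equivalence.** In a simulated data set with 13 per arm, the group-by-time F was 5.1116 on 1 and 24 df. The squared t on change scores was also 5.1116.

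**Formulas**, with N analysed in total:
- Change score: variance of the arm difference = (4/N) × 2(1−ρ).
- ANCOVA: (4/N) × (1−ρ²) × [1 + 1/(N−4)]. The bracket is the cost of estimating the slope: 1.044 at N = 26.8 and 1.028 at N = 40.
- Large-sample ratio, change score to ANCOVA: 2(1−ρ)/(1−ρ²) = 2/(1+ρ) = 1.54, 1.33, 1.18, 1.05.
- Dividing by the bracket gives the ratios below. Half-widths use t on N−2 df (change) and N−3 df (ANCOVA).

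| ρ | Variance ratio, N = 26.8 | Half-width in SD, change → ANCOVA | Variance ratio, N = 40 | Half-width in SD, change → ANCOVA |
|---|---|---|---|---|
| 0.3 | 1.47 | 0.94 → 0.78 | 1.50 | 0.76 → 0.62 |
| 0.5 | 1.28 | 0.80 → 0.71 | 1.30 | 0.64 → 0.56 |
| 0.7 | 1.13 | 0.62 → 0.58 | 1.14 | 0.50 → 0.46 |
| 0.9 | 1.01 | 0.36 → 0.36 | 1.02 | 0.29 → 0.28 |

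Worked line for ρ = 0.5, N = 26.8: SE(change) = √(4/26.8 × 1) = 0.386, and × 2.060 = 0.796. SE(ANCOVA) = √(4/26.8 × 0.75 × 1.044) = 0.342, and × 2.065 = 0.706.

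**In participants, at ρ = 0.5.** To match ANCOVA, the change score needs 26.8 × 0.277 = 7.4 more people at 27 analysed, or 40 × 0.297 = 11.9 more at 40.

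**Break-even.** Equal variances occur at ρ = (N−5)/(N−3): 0.916 at 26.8 and 0.946 at 40. For CI width the values are 0.908 and 0.942.

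**Power, for scale** (two-sided 5%, 13 per arm, ρ = 0.5; d assumed for medium and large): change score against ANCOVA, 23% against 28% at d = 0.5 and 50% against 60% at d = 0.8.

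**Unequal SDs.** With week-9 SD equal to k times the baseline SD, the change variance is 1 + k² − 2kρ and the ANCOVA residual is k²(1−ρ²). The difference is (1−kρ)², never negative, so ANCOVA can lose no more than its small-sample factor: about 4% at 27, 3% at 40. At 26.8 the ratios are 1.91, 1.68, 1.53 and 1.58 for k = 0.8, and 1.26, 1.10, 0.99 and 0.98 for k = 1.2.

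**Dropout (secondary).** Simulated with 20 per arm, no true effect, 12,000 trials per setting and 33% dropout, which depends on the score in one arm only; these mechanisms are assumptions.
- *Dropout on baseline* (log-odds 1 per SD), listwise deletion: completers' baseline mean shifts by 0.277 SD, so the change-score bias is (1−ρ) × 0.277 = 0.19, 0.14, 0.08, 0.03 SD, below half a standard error. Type I error is 6.8%, 6.7%, 5.7%, 5.0%, against 5.2%, 5.3%, 5.0%, 4.8% for ANCOVA.
- *Same dropout, likelihood-fitted repeated-measures model without a baseline covariate*: bias 0.00, but variance still 1.30, 1.19, 1.09 and 1.01 times that of ANCOVA.
- *Dropout on the week-9 score*: ANCOVA is worse, with absolute bias 0.26, 0.21, 0.15, 0.06 SD against 0.19, 0.14, 0.09, 0.03 SD, and type I error 10.2%, 9.0%, 7.8%, 6.3% against 6.7%, 6.5%, 5.7%, 5.6%.

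**The case against.** The planned analysis is valid, so this prefers one sound method over another. That is correct, and it is why the point is an improvement and not an error.

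The gain depends on an unknown correlation. At 0.7 with 27 analysed, the half-width moves only from 0.62 to 0.58 SD, and at 0.9 it does not move. At d = 0.5 and correlations of 0.5 to 0.7, power rises by only 4 to 5 points (13 per arm). This stands as to size. The trade is still one-sided, since the possible loss is capped at about 4%.

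The 0.9 threshold needs equal SDs. If the week-9 SD is 20% larger, break-even on variance falls to about 0.68 (27 analysed) or 0.72 (40). This stands as a limit on the threshold, and the same cap applies beyond it.

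The change-score identity with missing week-9 data holds only under listwise deletion, which the plan does not specify. Under a likelihood fit the ratios shrink to 1.30, 1.19, 1.09 and 1.01: smaller, but in the same direction. The 33% also refers to completing the protocol, which need not mean 33% missing week 9; hence the figures for 40.

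The ANOVA sentence names no group term, so reading the randomised contrast as group-by-time is an inference. It is the natural one, since Hypothesis 2 compares arms. If an 18-week visit were included, the overall test would no longer be one t-test. The baseline-to-week-9 contrast would still be a difference in mean change, and by week 18 the wait-list has started the intervention.

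The dropout results do not favour ANCOVA under every mechanism, so they do not carry the recommendation.

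**Conclusion.** The concern holds. For the randomised baseline-to-week-9 comparison, the planned ANOVA amounts to a change-score t-test on complete pairs. It gives up precision unless the correlation is about 0.9 or higher, assuming equal SDs. The loss is moderate: 28% to 30% in variance at a correlation of 0.5, 13% to 14% at 0.7, and negligible at 0.9. The correlations are assumed, and the figures for 27 further assume that every non-completer lacks week 9 and is dropped from the analysis. The plan should be changed because the gain is nearly free, not because the present analysis is invalid. ANCOVA does not recover missing week-9 values and does not protect against dropout driven by later, unobserved mood.

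**What to change.** Replace the ANOVA sentence in C 6.7 with wording such as:

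> Week-9 positive affect, negative affect and depressive symptoms will each be compared between randomised arms by ANCOVA with the baseline value of the same measure as covariate. Everyone randomised who has a week-9 measure will be included, whatever their class attendance. Results will be reported as an adjusted difference and a standardised effect (difference divided by the pooled baseline SD), each with a 95% CI.

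A constrained longitudinal mixed model is an equivalent alternative.

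Supporting changes:
- Confirm which scale measures each of the three outcomes and that it is collected at both visits. C2.5 repeats only the questionnaires bolded in C.6.3, and bolding is not visible in the text available to us. The PHQ-8 is listed under screening in C.6.1.
- Ask all randomised participants for the week-9 measures, including those who stop attending.
- Extend the attrition reporting already planned in C 6.7 to show missing week-9 data and baseline scores by arm, and state the limits on missing data given above.
- Reconcile the 18-week between-group analyses in C 6.7 with the baseline and 9-week schedule in sections A and C.1.

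Cost: one degree of freedom per outcome (about 4% of variance at 27 analysed and 3% at 40, already in the figures) and no data beyond what the planned ANOVA needs. Some follow-up effort is needed to bring people who stop attending to a week-9 visit that is already planned and paid.
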